## 1.0 Background

### Cardiovascular complications in end stage renal disease (ESRD)

Patients undergoing maintenance hemodialysis (MHD) have a high risk of developing cardiovascular events. Cardiovascular death accounts for more than 40% of overall mortality in these patients. Depending on the age group, the risk of cardiovascular death is between 5 and 100 times higher than in the general population. Furthermore, the survival rate after myocardial infarction in patients on MHD is only 40% at one year. Pharmacological interventions that reduce the risk of cardiovascular events in the general population are ineffective in patients undergoing MHD. Two different prospective, placebo controlled studies did not show a protective effect of statins in ESRD patients despite significant reduction in LDL cholesterol. A more recent study showed that the combination of simvastatin/ezetimibe, while effective in CKD patients not on dialysis, did not reduce the occurrence of atherosclerotic events in patients on MHD. Similarly, the only prospective clinical trial of an ACE inhibitor showed no protective effect on cardiovascular events in these patients.

### Inflammation and oxidative stress: risk factors for cardiovascular events in ESRD

The increased incidence of cardiovascular events and cardiovascular death in ESRD cannot be explained by the traditional risk factors, (e.g. age, male, diabetes, hypertension, hyperlipidemia, and smoking). Other factors have been implicated in the pathogenesis of accelerated atherosclerosis in ESRD.

Among them oxidative stress and systemic inflammation may play a central role (Figure 1). Chronic inflammation is commonly observed in ESRD

Figure 1. Risk factors for cardiovascular risk in ESRD

patients. Inflammatory markers, particularly interleukin 1 (IL-1), interleukin 6 (IL-6), and tumor necrosis factor-alpha (TNF $\alpha$ ), are chronically elevated in patients with ESRD, even before initiation of MHD. HD procedure itself also induces an acute increase in circulating concentrations of inflammatory markers. These data suggest that both, chronic uremia and recurrent HD contribute to inflammation. Inflammatory cytokines also predict cardiovascular endpoints in patients with ESRD. For instance, interleukin 6 (IL-6) predicts mortality and correlates with the severity of carotid atherosclerosis. Oxidative stress occurs when the reactive oxygen species (ROS) production is higher than the antioxidant capacity and is common in patients undergoing MHD. Markers of oxidative stress are increased in ESRD. For example, F2-Isoprostanes levels are increased before, during, and after HD procedure. Other markers of oxidative stress correlate with mortality and morbidity in ESRD: plasmalogen is associated with increased mortality, and malonaldehyde correlates with history of cardiovascular disease. Inflammation and oxidative stress play a role in the pathogenesis of atherosclerosis and the interaction between these factors is complex. Regardless of the initial event (either oxidative stress or inflammation), ROS are present in the atherosclerotic wall. In turn, ROS induce the activation of signaling pathways including the nuclear factor kappa  $\beta$  (NF- $\kappa$  $\beta$ ) cascade. Activation of NF- $\kappa$  $\beta$  results in the expression of cytokines and cell adhesion molecules, leukocyte recruitment, and more ROS production in the atherosclerotic lesion.

[figure not shown]
## Mitochondrial dysfunction contribute to atherosclerosis, oxidative stress and inflammation in ESRD

The mitochondria are one of the main sources of ROS. Around 2% of oxygen is incompletely reduced by the mitochondria and converted into ROS. Superoxide is the main ROS produced by mitochondria, which is then converted by manganese superoxide dismutase into hydrogen peroxide (H2O2). H2O2 can then diffuse across the mitochondrial membranes or be decomposed by either glutathione peroxidase or catalase. ROS produced by the mitochondria can activate the NLRP3 inflammasome inducing the production of interleukins (e.g. IL-1 $\beta$ ). There is a clear association between atherosclerosis, inflammation, oxidative stress and mitochondrial dysfunction. Mitochondrial DNA mutations are more common in atherosclerotic aorta, with none or little damage in nuclear DNA. Furthermore, mitochondrial DNA mutations are significantly more frequent in hearts from patients with coronary disease compared to age-matched healthy subjects. Using magnetic resonance spectroscopy (MRS), previous studies have shown that patients undergoing MHD exhibit skeletal muscle mitochondrial dysfunction when compared to healthy individuals. But no study has compared patients with different stages of CKD. It has also been suggested that mitochondrial dysfunction worsen years after HD initiation; however, this hypothesis has not been tested yet. Nevertheless, previous studies have shown abnormalities on mitochondrial metabolism in skeletal muscles biopsies and in peripheral blood mononuclear cells (PBMCs) from patients with CKD. Mitochondrial dysfunction in skeletal muscle may also explain why patients with CKD exhibit poor exercise tolerance and rapid fatigability. It is still unknown if mitochondrial dysfunction is the result of intrinsic mitochondrial defects or changes in mitochondrial number. These two factors can be differentiated by measuring at the same time mitochondrial function and mitochondrial volume density, which has never done in patients with CKD. Mitochondrial volume density is usually measured with electron microscopy. Other methods that correlate with electron microscopy are fluorescent dyes, mitochondrial enzymes activities and mitochondrial DNA content (or mitochondria DNA copy number). The latter has recently been proposed as a potential marker of mitochondrial dysfunction. Accordingly, a recent study showed an inverse correlation between mitochondrial DNA copy number in PBMCs and survival rate in patients undergoing MHD, suggesting that mitochondrial dysfunction may play a role in all-cause mortality in ESRD.

## Bradykinin may play a role in oxidative stress and mitochondrial dysfunction

Hemodialysis activates the kallikrein-kinin system and the production of bradykinin.

Under normal physiological conditions, bradykinin exerts its effect through B2 receptors. Bradykinin has a dual effect over the cardiovascular system: it increases tPA release and inhibits platelet aggregation, but also increases oxidative stress and systemic inflammation. Very few studies, however, have studied the effect of bradykinin on oxidative stress and inflammation in ESRD patients. Our group showed that endogenous bradykinin contributes to increases in plasminogen activator inhibitor-1 and monocyte chemo-attractant protein 1 following HD, consistent with a pro-inflammatory effect. Thus, any

intervention that increases bradykinin, such as ACE inhibitors, may increase the inflammatory response to HD. In fact, the candidate has observed that one week treatment with the ACE inhibitor ramipril elicits a greater pro-inflammatory response compared to ARB valsartan in patients undergoing MHD. Bradykinin also increases ROS production in cardiomyocytes, endothelial cells, vascular smooth muscles and renal tubular cells. Studies in human coronary endothelial cells showed that bradykinin vasodilator effects depended on ROS production by NADPH oxidase. Other studies suggest that bradykinin increases the production of mitochondrial ROS. But little is known about the effect of bradykinin on mitochondrial function, especially in patients undergoing MHD.

### **Mitochondrial dysfunction in CKD.**

There is strong evidence that oxidative stress and inflammation correlate with cardiovascular events in ESRD patients. Mitochondrial dysfunction may be the cause of both oxidative stress and inflammation. Although many previous studies have studied mitochondrial function in patients with CKD, they have not evaluated the effect of progressive kidney disease and the contribution of HD on mitochondrial function. We are planning to study for the very first time, mitochondrial function *in vivo* in patients at different stages of CKD not yet on HD compared to patients with ESRD. This approach will allow us to study the role of progressive CKD on mitochondrial dysfunction. Furthermore, no study has simultaneously performed *in vivo* measurements of mitochondrial function and skeletal muscle biopsies in patients with ESRD. This methodology will allow us to correlate *in vivo* mitochondrial function with biochemical and ultra-structural changes in mitochondria. But we will also evaluate the contribution of the HD procedure on mitochondrial dysfunction. HD activates the kallikrein-kinin system, which increases bradykinin levels and may contribute to the increased oxidative stress and inflammation observed in these patients. Our preliminary data suggest that bradykinin contributes to mitochondrial dysfunction, which is also present in ESRD. Little is known about the relation among hemodialysis, mitochondrial function and bradykinin, however. Understanding the interplay among these factors would help us to direct therapeutic interventions to patients with ESRD.

## **2.0 Rationale and Specific Aims**

[figure not shown]
Approximately 500,000 people per year undergo maintenance hemodialysis (MHD) as renal replacement therapy for end stage renal disease (ESRD) in the United States (US). Patients undergoing MHD are more susceptible to cardiovascular morbidity and mortality. Factors such as systemic inflammation and increased oxidative stress may play a role in accelerated atherosclerosis in these patients. Mitochondria are the main energy machinery of the cell but also sources of reactive oxygen species (ROS) and oxidative stress. Mitochondrial dysfunction, by increasing oxidative stress and inflammation, has been implicated in the pathogenesis of atherosclerosis in the general population, and it has been described in patients on MHD. The etiology of mitochondrial dysfunction in ESRD is not clearly elucidated, but progressive chronic kidney disease (CKD) and MHD are the possible causes. While earlier studies have shown the presence of mitochondrial dysfunction in ESRD compared to healthy individuals, none has previously studied the role of progressive CKD on mitochondrial dysfunction. Several studies suggested that the decline in mitochondrial function occurs following initiation of MHD and that the hemodialysis (HD) procedure is a potential contributor to this process. HD activates the kallikrein-kinin system, which increases bradykinin formation. Bradykinin exerts cardio-protective effects such as vasodilatation and tissue plasminogen activator (tPA) release, but also increases inflammation and oxidative stress and eventually may lead to

mitochondrial dysfunction. In fact, our preliminary data suggest that bradykinin increases mitochondrial superoxide production in peripheral blood mononuclear cells (PBMCs) *in vitro*, and endogenous bradykinin increases plasma isofurans during HD. **The overarching goal of this study is to determine the role of progressive CKD and the activation of the kallikrein-kinin system during MHD on the development of mitochondrial dysfunction.** In order to achieve this goal, we propose the following specific aims:

**Specific Aim 1: Test the hypothesis that mitochondrial function worsens with the progression of CKD and initiation of HD.** We hypothesize that mitochondrial function gradually deteriorates with the progression of CKD. We also expect that MHD rather than preventing the decline worsens mitochondrial function. To test this hypothesis, we will measure *in vivo* mitochondrial function (half-time of phospho-creatinine recovery) using  $^{31}\text{P}$  magnetic resonance spectroscopy ( $^{31}\text{P}$ -MRS) in three groups of subjects: 1) patients with ESRD on MHD, 2) patients with CKD stages 3-5 but not on MHD and 3) control subjects without CKD. The subjects in each group will be matched by age, sex, race, diabetic status, and BMI. We will also evaluate changes in mitochondrial quantity by measuring markers of mitochondrial biogenesis and mitochondrial density in muscles biopsies. We anticipate that patients on MHD exhibit the worst mitochondrial function (*i.e.* the longest half time of phosphocreatinine recovery).

**Specific Aim 2: Test the hypothesis that endogenous bradykinin promotes mitochondrial dysfunction in patients undergoing MHD.** To test this hypothesis, we will conduct a randomized, double-blind, placebo-controlled, 2x2 crossover study, comparing HOE-140, a bradykinin B2 receptor blocker, and placebo administered 1 hour prior to beginning of HD session and during HD. Mitochondrial function will be measured using  $^{31}\text{P}$ -MRS. We anticipate that bradykinin B2 receptor blockade with HOE-140 will improve mitochondrial function during HD.

Understanding the mechanisms leading to mitochondrial dysfunction is an important step in terms of developing new strategies to prevent cardiovascular morbidity and mortality in ESRD. The candidate is in unique position to accomplish this project based on his training in mitochondrial physiology, clinical pharmacology and clinical trials. The proposed studies will develop the candidate credentials to become an independent and successful physician scientist.

**Figure 3. A.** Mitochondrial copy number in healthy controls, hypertensive subjects without history of ESRD (HTN) and chronic HD patients (n=8 in each group, \*p<0.05 compared to chronic HD group). **B.** Correlation between mtDNA copy number and F2-Isoprostanes in ESRD patients measured 2 hours after the end of HD (n=8).

### 3.0 Animal Studies and Previous Human Studies

[figure not shown]
#### 3A Mitochondrial DNA copy number in chronic hemodialysis

Mitochondrial DNA (mtDNA) is susceptible to damage by oxidative stress due to the lack of histone protection. mtDNA mutations and reduced mtDNA copy number are

[figure not shown]
commonly present in cells exposed to excessive concentration of ROS. Using qPCR we measured mtDNA copy number in white blood cells from patients on MHD, as previously described (Figure 3A). Copy number was significantly decreased in patients on MHD compared to healthy and hypertensive subjects, matched by age, sex, race and BMI. Furthermore, there was a trend toward negative correlation between mtDNA copy number and F2-Isoprostanes (Figure 3B), suggesting that oxidative stress may play a role in the observed reduction of mtDNA copy number.

### 3B Markers of oxidative stress are increased in patients undergoing chronic hemodialysis

F2-Isoprostanes and Isofurans, products of non-enzymatic oxidation of arachidonic acid, are reliable measures of oxidative stress in plasma. Formation of either F2-Isoprostanes or Isofurans depends on tissue oxygen tension. In conditions of high oxygen tension the formation of Isofurans is favored. This may occur due to increased oxygen delivered (breathing a high FIO2) or decreased oxygen consumption (as in mitochondrial dysfunction). Previous studies showed that F2-Isoprostanes are increased in patients undergoing MHD. We also found that the levels of Isofurans were higher in patients undergoing MHD than in patients undergoing cardiac surgery (Figure 4A). Furthermore, the increased ratio of Isofurans to F2-Isoprostanes suggests a preferential production of Isofurans in patients undergoing MHD (Figure 4B). These findings may be a consequence of mitochondrial dysfunction, as previously suggested.

**Figure 4.** Isofurans levels (A) and ratio of Isofurans (IsoF) to F2-Isoprostanes (IsoP) (B) in patients undergoing chronic HD compared to a cohort of patients that underwent cardiac surgery.

[figure not shown]
**Figure 5.** A Isofurans levels during HD in patients receiving HOE-140 or placebo. B. Mitochondrial superoxide levels, measured using MitoSOX™ in peripheral blood mononuclear cells (PBMCs) with and without bradykinin stimulation.

### 3C. Role of bradykinin in oxidative stress during hemodialysis

Our group has previously shown that, during HD, blockade of endogenous bradykinin, through the bradykinin B2 receptor antagonist HOE-140, decreases markers of inflammation. We also found that HOE-140 decreases the formation of Isofurans during HD, suggesting that endogenous bradykinin contributes to oxidative stress in patients undergoing HD (Figure 5A). Using isolated PBMC from healthy individuals and patients undergoing MHD, we found that bradykinin increased mitochondrial superoxide production (Figure 5B). These preliminary results suggest a role of bradykinin on mitochondrial ROS production.

### 3D. Mitochondrial ultrastructure in patients undergoing MHD

Mitochondrion ultra-structure was also evaluated in muscle biopsy from 5 different patients undergoing MHD. Figure 6 shows some of representative electron micrographs of normal mitochondria (Figure 6A) and abnormal mitochondria with signs of cristae swelling (Figure 6B). There also were many double membrane formations compatible with auto-phagosomes, which are surrounding structures that resemble mitochondria (Figure 6C). This suggests that mitophagy, a particular type of autophagy, may be increased in patients undergoing HD. We also found many lipofuscin granules (Figure 6D), probably as result of oxidative damage of mitochondria and lysosomes.

**Figure 6.** Representative electron micrograph of skeletal muscles from patients undergoing MHD. **A.** Normal sub-sarcolemmal mitochondria. **B.** Mitochondria with signs of swelling. **C.** Double membrane structure compatible with auto-phagosome. **D.** Lipofuscin pigment (scale bar=500 $\mu$ m).

## 4.0 Inclusion/Exclusion Criteria

### Inclusion Criteria

1. Age 18 years or older.
2. On thrice-weekly chronic hemodialysis for at least 6 months.
3. Clinically stable, adequately dialyzed (single-pool Kt/V > 1.2) thrice weekly, with polysulphone membrane for at least 3 consecutive months prior to study.
4. For Specific Aim 1 only: Chronic kidney disease stages 3-5 but not yet on hemodialysis (eGFR less than 59 mL/min per 1.73 m^2), or subjects with no history of CKD.
5. Negative serum pregnancy test

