## **6.0 Study Procedures**

**Specific Aim 1: Test the hypothesis that mitochondrial function worsens with the progression of CKD and initiation of HD**

### ***Population***

Three different groups of patients will be evaluated: 1. Patients with ESRD and on MHD for at least 6 months, 2. Patients with CKD stages 3-5 (eGFR less than 59 mL/min per 1.73 m^2) not yet on MHD and who have visited a nephrologist at least 1 month prior to enrollment, and 3. Control subjects with no CKD. The subjects in each group (including the controls) will be matched by age, sex, race, diabetic status, and BMI. All participants will be adults 18-75 years of age.

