### General protocol

After obtaining informed consent, the investigators will perform a physical examination.

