## **10.0 Statistical Considerations**

### ***Statistical Analysis***

#### ***a. Sample size***

- *Specific Aim 1:* We plan to enroll 3 groups: patients with ESRD on MHD (group 1), patients with CKD stages 3-5 but not on MHD (group 2), and control subjects without CKD (group 3). In previous studies, the half-time of PCr recovery in HD patients following exercise was 1.1 minutes (m) and the standard deviation was 0.35 m. Normal values are 0.6 m with a standard deviation of 0.24 m. Assuming the same coefficient of variation, we anticipate the mean±SD of the half-time of PCr recovery would be 1.1±0.35m, 0.85±0.27m, and 0.6±0.19m, for groups 1, 2 and 3, respectively. Using a 2-sample t-test, we will need 26 subjects per group to have 80% power to detect the difference between groups 1 and 2, and 15 subjects per group to detect the difference between groups 2 and 3 with a type I error rate of 0.05. For matching purposes, we plan to study 26 subjects in each group. The subjects will be matched by age, race, gender, BMI, diabetic status.

- Specific Aim 2: The primary end-point is the half-time of PCr recovery (in minutes) measured by  $^{31}\text{P}$ -MRS. Samples sizes were calculated using data from previous studies. A sample size of 11 will have 80% power to detect a difference in means (of the half time of PCr recovery) of 0.33 minutes (the placebo treatment mean of  $1.1\pm 0.35$  minutes and the HOE-140 treatment mean of  $0.77\pm 0.35$  minutes, a 30% reduction), assuming a correlation coefficient of 0.5 between the two measures, and that results to a standard deviation of differences of 0.35, using a paired t-test with a 0.05 two-sided significance level.

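### Aim 1 controls are admitted on absence of a CKD history, with no stated kidney-function measurement to confirm the intended absence of CKD

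*Combined protocol and SAP*

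**What the plan says.** The protocol describes the Aim 1 control group in two ways.

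- **Section 4.0, Inclusion Criteria, item 4** covers the CKD and control groups together. The CKD group has a numeric limit: "Chronic kidney disease stages 3-5 but not yet on hemodialysis (eGFR less than 59 mL/min per 1.73 m 2". Controls enter as "or subjects with no history of CKD".
- **Section 6.0, Specific Aim 1, Population** has "Control subjects with no CKD", and **Section 10.0, Sample size** has "control subjects without CKD (group 3". Section 2.0 likewise describes controls as being without CKD.

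On procedures, the Aim 1 general protocol opens with "After obtaining informed consent, the investigators will perform a physical examination". Eligibility also uses two laboratory values, a serum pregnancy test (inclusion item 5) and serum albumin (Aim 1 exclusion item 22). No creatinine, eGFR or urine marker is named for controls among the eligibility criteria, the procedures or the Aim 1 endpoint table.

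On matching, Section 6.0 states: "The subjects in each group (including the controls) will be matched by age, sex, race, diabetic status, and BMI". Sections 2.0 and 10.0 (Sample size) give the same factors. The Data analysis plan gives a different list, which includes the cause of kidney disease, a factor that controls without CKD cannot have.

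**The concern.** A history of CKD and the presence of CKD are different conditions. Someone whose kidney function has never been tested has no history of CKD, whatever the eGFR. Kidney function is the exposure that Aim 1 studies, so it should be confirmed in every group whose label depends on it.

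Matching makes the gap more relevant. Controls resemble CKD and dialysis patients in age, BMI and diabetic status, so they are not a deliberately low-risk group.

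The plan expects half-time of PCr recovery to lengthen as kidney disease advances. On that expectation, controls with unrecognised low eGFR would raise the control mean and shrink both contrasts that use it: group 2 versus 3 and group 1 versus 3. The plan reports point estimates with 95% confidence intervals, and enrolling more subjects would not remove this bias. The planned comparability check and ANCOVA would not remove it either, because no kidney-function value is named for controls.

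**Working it through.** **Inputs from the plan.** Section 10.0 anticipates that the mean±SD half-time in minutes "would be 1.1±0.35m, 0.85±0.27m, and 0.6±0.19m, for groups 1, 2 and 3, respectively". It concludes "we will need 26 subjects per group to have 80% power to detect the difference between groups 1 and 2", and 15 per group for groups 2 versus 3, at a type I error of 0.05. The plan is to study 26 per group.

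**Step 1: reproduce the plan's sizes.** Two-sample t-test, pooled SD = √((s₁² + s₂²)/2), noncentrality = difference / (pooled SD × √(2/n)), df = 2n − 2. Sidedness is not stated for Aim 1. Two-sided reproduces the figures; one-sided would give 21 and 12.

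- Groups 1 v 2: pooled SD = √((0.1225 + 0.0729)/2) = 0.3126. At n = 26, noncentrality = 2.884 and power = 80.7%. The stated 26 is reproduced.
- Groups 2 v 3: pooled SD = √((0.0729 + 0.0361)/2) = 0.2335. At n = 15, noncentrality = 2.933 and power = 80.8%. The stated 15 is reproduced.
- Groups 2 v 3 at the planned n = 26: noncentrality = 3.861 and power = 96.6%.

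**Step 2: dilution model.** Let f be the share of controls with unrecognised low eGFR, with mean μ and SD s. The rest follow 0.6±0.19.

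- Control mean = 0.6 + f(μ − 0.6)
- Control variance = (1 − f)(0.19²) + f s² + f(1 − f)(μ − 0.6)²

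The documents do not give f, so 5%, 10% and 20% are assumptions (about 1, 3 and 5 of 26 controls). Two cases are taken for μ:

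- *Like the CKD group:* μ = 0.85, s = 0.27.
- *Halfway:* μ = 0.725. At the plan's constant coefficient of variation, s = 0.725 × 0.35/1.1 = 0.23.

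Worked example, f = 20%, like the CKD group: mean = 0.6 + 0.2 × 0.25 = 0.65. Variance = 0.8 × 0.0361 + 0.2 × 0.0729 + 0.16 × 0.0625 = 0.0535, so SD = 0.231. Difference = 0.85 − 0.65 = 0.20. Pooled SD = 0.2514, noncentrality = 2.869, power = 80.3%.

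**Step 3: results for groups 2 v 3 at 26 per group.**

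| f | Difference, like CKD (min) | Power | Difference, halfway (min) | Power |
|---|---|---|---|---|
| 0% | 0.250 | 96.6% | 0.250 | 96.6% |
| 5% | 0.238 | 94.1% | 0.244 | 95.6% |
| 10% | 0.225 | 90.5% | 0.238 | 94.4% |
| 20% | 0.200 | 80.3% | 0.225 | 91.3% |

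Simulating the like-CKD case (40,000 runs) gave 96.6%, 90.2% and 79.6% at f = 0, 10% and 20%, in line with the formula.

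**Step 4: the other contrasts.** Groups 1 v 3 lose the same absolute amount from a larger difference. In the like-CKD case, 1.1 − 0.6 = 0.50 becomes 0.488, 0.475 or 0.45 min. Groups 1 v 2 use no controls, so nothing changes.

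**The case against.** The strongest reply is that the protocol plainly intends controls without CKD. Item 4 is a combined list, and the group descriptions elsewhere would exclude a person with a known eGFR below 59. That stands as a reading of intent. A reader might infer that the protocol deliberately accepts controls with low eGFR, and the documents do not support this. What remains is that the eligibility item asks only about history, and no procedure is named that would reveal the problem.

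Silence about creatinine is also weak evidence that it will not be measured. No screening creatinine is named for group 2 either, although that group has an eGFR limit. Pregnancy and albumin values are required without appearing in the general protocol. This stands too, so the finding is that confirmation is unspecified, not that it will be omitted.

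A reader might also infer that Aim 1 is underpowered or that its whole study of progression is compromised. Neither follows. Groups 2 v 3 needed 15 per group and 26 are planned, so power is still about 80% at 20% misclassified even in the less favourable case. The contrast that sets the sample size is untouched. The bias runs towards no difference, so under the plan's hypothesis it would not create a false positive. Undiagnosed disease may also be milder than that of the CKD group, which is why the halfway case is shown; it halves the loss in the difference.

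**Conclusion.** The concern holds as a minor, easily corrected design point. The history-based eligibility item does not secure the CKD-free group described in Sections 2.0, 6.0 and 10.0, and no measurement is named to close the gap.

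The consequence is possible attenuation of the two control contrasts. For groups 2 v 3 the loss is 5% to 20% of the assumed difference if misclassified controls resemble the CKD group, and 2.5% to 10% if they lie halfway, over assumed shares of 5% to 20%. Those shares are illustrative; nothing in the documents says how many controls would be affected, or whether any would. The direction rests on the plan's hypothesis that recovery slows as kidney function falls. The main gain from a change is an estimate protected from this bias; the gain in power is secondary.

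**What to change.** Reconcile Section 4.0, item 4, with Section 6.0. Require each Aim 1 control to have both no history of CKD and a measured eGFR not below the upper bound used for group 2. Take the creatinine at screening with the other eligibility bloods, and have the result before spectroscopy and biopsy and before the matched triplet is formed. Relying on the study-day sample risks finding a control ineligible after the biopsy and breaking a triplet. Report eGFR by group.

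An eGFR floor alone does not exclude CKD stages 1–2. The protocol should either say that group 3 means no stage 3–5 disease or name the further marker it will use.

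The cost is one creatinine per control and a few volunteers found ineligible at screening. The sample size need not change.
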